#### **7.9. *Curative Intent Surgery – Office Visit***

- Patient's overall health status
- Assessment of Biliary Obstructive Symptoms
  - Right Upper Quadrant Pain
  - Fever/Chills
  - Jaundice
  - Itching
  - Dark urine
  - Pale stools
  - Nausea/Vomiting
- Operative Details
- Stent Removal
- Surgical Complications including intraoperative blood loss
- Intra- and Post-Operative Transfusion
- Post-Operative Course
- Specimen Pathology
- Administered Neoadjuvant therapy
- Adverse events and reinterventions (as applicable)
- Device Events (as applicable)

#### **7.10. *Transition to Palliative Management Visit (as needed) – Phone and/or Office Visit***

- Assessment of Biliary Obstructive Symptoms
  - Right Upper Quadrant Pain
  - Fever/Chills
  - Jaundice
  - Itching
  - Dark urine
  - Pale stools

- Nausea/Vomiting
- Laboratory Liver Function Tests (LFTs)
  - Serum Albumin level
  - Total Bilirubin
  - Alkaline Phosphatase
  - SGPT (ALT)
- Adverse Events (as applicable)
- Device Events (as applicable)

**7.11. *Post-Operative Follow-Up Visit (30 days) – Phone and/or Office Visit***

- Day 30 Post-Surgery Visit
- Patient's overall health status
- Assessment of Biliary Obstructive Symptoms
  - Right Upper Quadrant Pain
  - Fever/Chills
  - Jaundice
  - Itching
  - Dark urine
  - Pale stools
  - Nausea/Vomiting
- Adverse events and reinterventions (as applicable)
- Device Events (as applicable)

**7.12. *Long Term Follow-Up Visit (1 year after initial treatment for patients that have transitioned to palliation or 1 year post-stent placement for patients that have not undergone surgery or transitioned to palliation (with or without Neoadjuvant Therapy) – Phone and/or Office Visit***

- For patients not undergoing surgery
- Patient's overall health status
- Assessment of Biliary Obstructive Symptoms
  - Right Upper Quadrant Pain
  - Fever/Chills
  - Jaundice
  - Itching
  - Dark urine
  - Pale stools
  - Nausea/Vomiting
- Laboratory Liver Function Tests (LFTs)
  - Serum Albumin level
  - Total Bilirubin
  - Alkaline Phosphatase

- SGPT (ALT)
- Adverse events and reinterventions (as applicable)
- Device Events (as applicable)

### 7.13. *Study Completion*

End of study will be reached at:

- Up to 30 days post-surgery for those patients undergoing potential curative intent surgery
- 1 year post stent placement for patients that have transitioned to palliation within 12 months after stent placement
- 1 year post stent placement for patients who do not undergo potential curative intent surgery and do not transition to palliation within 12 months after stent placement (with or without Neoadjuvant Therapy)

End of study will be reached at study completion, at patient withdrawal from study, or at death, whichever comes first.

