### 3.1. Scale and Duration

Patients that have gone to surgery will be followed for 30 days post-surgery. For patients that have transitioned to palliation, the Long Term Follow-Up Visit will occur one (1) year after initial treatment. Patients that have not gone to surgery and have not transitioned to palliation (with or without Neoadjuvant Therapy) will be followed up to 1 year post-stent placement. There will be 6-12 participating centers with anticipated enrollment of 122 patients.

At each investigational center, there will be one principal investigator (PI) who will be an endoscopist. Where possible at least one co-investigator should be a pancreaticobiliary surgeon.

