### 4.2. Secondary Endpoints

1. Occurrence and severity of adverse events related to the stent and/or stenting procedure
2. Occurrence and severity of surgical complications
3. Occurrence and severity of peri-surgical complications (up to 30 days after surgery)
4. Ability to deploy the stent in satisfactory position across the stricture (Stent Placement Success)
5. Improvement of biliary obstructive symptoms during stent indwell at Week 1 and Monthly until surgery or transition to palliation as applicable, compared to Baseline
6. Improvement of Laboratory Liver Function Tests (LFTs) until surgery for patients undergoing surgery, and at Week 1 and Monthly until transition to palliation, and at 1 year after stent placement for patients not undergoing surgery
7. Biliary Reintervention rate
8. Ability to complete neoadjuvant therapy as intended without stent related interruptions of neoadjuvant therapy
9. Stent migration rate
10. Assessment by surgeon of interference, if any, of SEMS on time to surgery and/or success of pancreaticoduodenectomy
11. For patients transitioning to palliative management: Successful biliary drainage defined as absence of reinterventions for the management of biliary obstructive symptoms from stent placement to 1 year after stent placement

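### Sections 3.1, 7.12 and 7.13 give two end-of-study dates, with no precedence, for a patient who has curative-intent surgery without resection and then becomes palliative

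*Protocol*

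**What the plan says.** Protocol 7.13 defines three ends of study:

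- Surgery: "Up to 30 days post-surgery for those patients undergoing potential curative intent surgery".
- Palliation: "1 year post stent placement for patients that have transitioned to palliation within 12 months after stent placement".
- Neither: also 1 year after stent placement, for "patients who do not undergo potential curative intent surgery and do not transition to palliation within 12 months after stent placement".

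A closing sentence adds: "End of study will be reached at study completion, at patient withdrawal from study, or at death, whichever comes first".

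Section 3.1 has the same first two rules: "Patients that have gone to surgery will be followed for 30 days post-surgery", and then "For patients that have transitioned to palliation, the Long Term Follow-Up Visit will occur one (1) year after initial treatment".

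The heading of 7.12 gives the long-term visit to patients who have moved to palliation, and to those with neither surgery nor palliation. Its first bullet limits the visit differently: "For patients not undergoing surgery".

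Secondary endpoint 11 (protocol 4.2, repeated in SAP 5.1) applies to patients moving to palliative management. It defines success as "absence of reinterventions for the management of biliary obstructive symptoms from stent placement to 1 year after stent placement".

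**The concern.** The rules treat surgery and palliation as alternatives, but one patient can have both: taken to surgery with curative intent, not resected, and then managed palliatively. That patient has two end-of-study dates.

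If a site follows the surgery rule, the patient leaves about 30 days after the operation. A reintervention before then is already recorded and makes the patient an endpoint 11 failure. A patient still event-free at close-out has an unobserved remainder of the 1-year window. That patient must then be dropped from endpoint 11 or counted as a success on partial follow-up. SAP 7.3 reports binary rates per patient, and neither document says how to count an endpoint 11 patient with incomplete follow-up. Protocol 8.4 mentions censored-data models and missing-data sensitivity analyses only in general terms, and SAP 3.1.3 places them under the primary endpoint.

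With 6–12 sites, the conflict may also be resolved differently from site to site. Follow-up that was never collected may not be recoverable later.

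**Working it through.** The plan has no figure of its own to reproduce here. The check compares the rules and then sizes the gap under stated assumptions.

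**1. Rules for a patient explored, not resected, then palliated**

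| Place | What applies | Surgical patients excluded from the 1-year rule? |
|---|---|---|
| 7.13, bullet 1 | up to 30 days after surgery | – |
| 7.13, bullet 2 | 1 year after stent placement | no |
| 3.1, surgery sentence | 30 days after surgery | – |
| 3.1, palliation sentence | visit 1 year after initial treatment | no |
| 7.12 heading; synopsis visit list; Table 3 footnote | 1-year visit for palliated patients | no |
| 7.12, first bullet | 1-year visit | yes |
| 4.2, endpoint 11 | outcome to 1 year after stent placement | no |

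The third bullet of 7.13 excludes surgical patients in so many words and the second does not. The text therefore gives no ground for reading a surgery exclusion into the palliation rule.

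**2. Precedence.** The closing sentence of 7.13 takes the earliest of study completion, withdrawal and death. It does not say which bullet defines completion when two apply, so it does not settle the matter.

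**3. Is the patient foreseeable?** The documents never mention one. They do call the surgery potentially curative (7.13, 8.4.4), collect a surgical assessment of tumor invasion (Table 3) and ask about the success of the pancreaticoduodenectomy (PD; endpoint 10). Surgery that does not end in resection is within what they contemplate.

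**4. Follow-up lost if the surgery rule is applied.** With surgery at month m after stenting, follow-up ends at about m + 1.

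Unobserved months = max(0, 12 − (m + 1)) = max(0, 11 − m)

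Section 1 gives 2–7 months of neoadjuvant therapy and a rest and restaging period of up to several months. Taking that period as 1–3 months (an assumption) gives m = 3 to 10.

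- m = 3: 11 − 3 = 8 months unobserved
- m = 10: 11 − 10 = 1 month
- m = 11 or later: none

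If the palliation rule is applied, nothing is lost at any m.

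**5. Number of patients.** Section 1 says 25%–41% do not reach PD as planned because of events between diagnosis and the scheduled operation. Call this q and treat it as loss before surgery. Let a be the share of explored patients not resected. The documents give no value, so 10%–20% is an assumption.

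Explored E = 122 × (1 − q); affected A = E × a

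| q | E | A at a = 10% | A at a = 20% |
|---|---|---|---|
| 41% | 122 × 0.59 = 72.0 | 7.2 | 14.4 |
| 25% | 122 × 0.75 = 91.5 | 9.2 | 18.3 |

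The range is about 7–18 patients. If everyone lost before surgery also becomes palliative, their share of the endpoint 11 population is A / (A + 122q). The lowest value is 7.2 / (7.2 + 50.0) = 13% and the highest is 18.3 / (18.3 + 30.5) = 38%.

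These patients fall under both rules. Fewer would lose data: only those alive and event-free at close-out, with surgery before about month 11, at a site that applies the surgery rule.

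**The case against.** The strongest reply is that a consistent reading exists. The surgery visit in 7.9 lists stent removal and specimen pathology, and SAP 5.4 contrasts surgery with palliation as separate classes. If surgery means resection, an unresected patient simply follows the palliation rule to 1 year. This reading is reasonable and a site may well adopt it. It is not stated, however. The phrase about potential curative intent describes the aim of the operation rather than its result, and the first bullet of 7.12 turns on having had surgery.

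A reader might go further and infer that 7.13 ends this patient's follow-up at 30 days, so that endpoint 11 cannot be observed. The documents do not support that. The second bullet of 7.13, the second sentence of 3.1, the 7.12 heading, the synopsis visit list and the Table 3 footnote all give the 1-year follow-up without excluding surgical patients.

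Three further inferences also go too far:

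- **The stent stays in place.** Section 1 describes en-bloc removal in patients who undergo PD. No passage says what happens without resection, so retention is an inference.
- **The loss selects patients whose stent worked.** Section 6 allows a new stent after failure during neoadjuvant therapy, so a patient can reach surgery after a reintervention.
- **The 25%–41% already contains aborted resections.** That gives A = a × 122(1 − q)/(1 − a), or about 8–23 patients. Section 1 places those losses before the scheduled operation. At the top of that range 122 × 0.75/0.80 = 114 patients would be explored, leaving under 7% lost beforehand.

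It is also fair that endpoint 11 is the last of eleven secondary endpoints and has no hypothesis test.

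**Conclusion.** The concern holds as an unresolved overlap. A patient who has curative-intent surgery without resection and then becomes palliative has two end-of-study dates, no rule ranks them, and 7.12 disagrees with its own heading. Whether endpoint 11 is observed to 1 year in that patient depends on how the site reads the text.

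About 7–18 of 122 patients could be affected, each losing at most about 8 months of the window. The count rests on an assumed 10%–20% of explored patients not resected and on reading the 25%–41% as loss before surgery. The time lost rests on surgery at months 3–10. The contradiction itself needs none of these assumptions.

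The primary endpoint is unaffected, because its window closes at surgery or at transition to palliation. This is a modest, inexpensive improvement to a secondary endpoint.

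**What to change.** Reconcile 3.1, 7.12 and 7.13 so that they state one rule:

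- The 30-day end of study applies only after completed resection with stent removal.
- A patient explored but not resected who transitions to palliation has the 30-day post-operative visit, stays in follow-up to 1 year after stent placement, and counts in endpoint 11.
- The primary endpoint window for that patient still ends at surgery.
- The first bullet of 7.12 is brought into line with its heading.

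The cost is a short protocol amendment and one additional long-term contact for this subgroup, which 7.12 already allows by phone. No procedure is added.

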## 8. Statistical Considerations

### 8.1 *Hypotheses*

Compared to the use of an Uncovered SEMS, use of a Fully Covered SEMS may present a higher risk of migration, but offers the ability to remove the stent were this deemed indicated by the treating endoscopist. Statistical testing will be performed to determine if the rate of success when using the Fully Covered SEMS is non-inferior to the rate of success when using the Uncovered SEMS. The following hypothesis will be tested:

$$H_0: \pi_{UC} - \pi_{FC} \geq \Delta \text{ (Inferior)}$$

$$H_a: \pi_{UC} - \pi_{FC} < \Delta \text{ (Non-inferior)}$$

where  $\pi_{FC}$  and  $\pi_{UC}$  are the probabilities of having success in the WallFlex Fully Covered Stent and WallFlex Uncovered Stent arms respectively, and  $\Delta$  is defined as the non-inferiority margin.

### 8.2 *Sample Size*

The sample size was calculated for the test using an exact non-inferiority test in StatXact 9® software. The non-inferiority margin ( $\Delta$ ) is set at 20%. Each arm is assumed to have a success rate of 80.5%, which is the lower 95% CI boundary from the meta-analysis, which is

done below. Given these assumptions a sample size of  $51 \times 2 = 102$  patients provides 80% power to reject the null hypothesis listed above. If the p-value calculated for the test is below 0.05 it will be concluded that the test is significant and that the WallFlex Fully Covered stent is non-inferior to the WallFlex Uncovered stent.

In order to compensate for possible loss of patients to follow-up or per Endoscopist's decision to select the Uncovered stent based on ductal anatomy, namely stricture involving the low cystic duct confluence, an additional 20% of patients will be enrolled giving a total sample size of 122 patients.

The success rate estimate is extracted from a full literature search which yielded nine articles (377 patients) on the use metal stents for pre-operative biliary drainage. The nine articles yielded a success rate estimate of 84.6% with a 95% CI of (80.5%, 87.9%).

### **8.3 Analysis Populations**

#### **8.3.1 Enrolled Cohort**

A patient is considered "enrolled" after signing the study-specific ICF. Patients who sign the ICF but subsequently do not meet one or more of the eligibility criteria provided in Section 5.1 and Section 5.2 will be considered screen failures and excluded from the study.

#### **8.3.2. Intent-to-Treat Cohort**

This cohort consists of those "enrolled" patients who meet all inclusion/exclusion criteria and are subsequently randomized.

#### **8.3.3. Per-Protocol Cohort**

The per-protocol cohort is a subset of the ITT patients who are treated per protocol and have no major protocol deviations (per ICH E9 definitions).

### **8.4 Data Analysis**

All statistical analyses will be done using The SAS System software, version 8 or higher (Copyright © 2000 SAS Institute Inc., SAS Campus Drive, Cary, North Carolina 27513, USA. All rights reserved).

The distribution of prognostic factors between patients with and without data will be examined. Statistical models that account for censored data will be employed in appropriate circumstances, e.g. for time-to-event outcomes. Sensitivity analyses will be conducted to assess the impact of missing data on the interpretation of the results, e.g. a tipping point analysis.

#### **8.4.1. Baseline Data**

Patient demographics, clinical history, risk factors, obstructive symptoms, LFTs, tumor diagnosis, patient overall health, neoadjuvant therapy, and assessment of tumor invasion will be summarized using descriptive statistics (e.g., mean, standard deviation, n, minimum, maximum) for continuous variables and frequency tables for discrete variables.

#### **8.4.2. Post Procedure Data**

Post-procedure information will be collected at regularly scheduled follow-up examinations as detailed in the clinical study event schedule and will be summarized using descriptive statistics for continuous variables (e.g., mean, standard deviation, n, minimum, maximum) and frequency tables or proportions for discrete variables.

#### **8.4.3. Interim Analyses**

No formal interim analyses are planned for this study.

#### **8.4.4. Subgroup Analyses**

Stratified analyses will include tabulating the primary endpoint and select secondary endpoints by patients that undergo potentially curative surgery versus transition to palliation, by bilirubin level above or below 3 mg/dL, and gender.

#### **8.4.5. Justification of Pooling**

The analyses will be performed using data pooled across institutions. An assessment of the poolability of patients across sites will be made by fitting generalized linear models with site as the factor of interest and the primary endpoint as the outcome.

#### **8.4.6. Multivariable Analyses**

Univariate and multivariate analyses may be performed to assess the effect of potential predictors on the primary endpoint using logistic regression or Cox Proportional Hazards regression.

Variables from the following categories will be considered as possible predictors: demographics, tumor diagnosis, baseline LFTs, neoadjuvant therapy protocol, obstructive symptoms, baseline health status, and medical history. Factors from the univariate model with  $p \leq 0.20$  will also be modeled multivariately using a stepwise procedure in a generalized linear model or Cox Proportional Hazards regression model. The significance thresholds for entry and exit into the model will be set to  $p \leq 0.10$ .

#### **8.4.7. Changes to Planned Analyses**

Any changes to the planned statistical analyses made prior will be documented in an amended Statistical Analysis Plan.

## 9. Potential Risks and Benefits

### 9.1. *Anticipated Adverse Device Effects*

The following anticipated adverse device effects (ADE) should be reported only if they are related to the stent and/or stenting procedure. They have been identified for the WallFlex Biliary FC and UC Stent, as indicated in the commercial Directions for Use (DFU) and may include, but are not limited to:

- Pain
- Bleeding
- Fever
- Nausea
- Vomiting
- Infection
- Inflammation
- Recurrent obstructive jaundice
- Stent occlusion
- Tumor overgrowth around ends of stent
- Tumor ingrowth through the stent
- Mucosal hyperplasia
- Cholangitis
- Cholecystitis
- Pancreatitis
- Ulceration of duodenum or bile duct
- Perforation of duodenum or bile duct
- Stent migration
- Death (other than that due to normal disease progression)
- Stent misplacement
- Perforation of the gallbladder due to the stent covering the cystic duct
- Stent Fracture
- Hepatic abscess

### 9.2. *Anticipated Surgical Adverse Events*

- Pancreaticojunostomy leakage
- Hepaticojunostomy leakage

- Gastro-duodenojejunostomy leakage
- Delayed gastric emptying
- Biliary leakage
- Intra-abdominal abscess formation
- Wound infection
- Portal Vein Thrombosis
- Cholangitis
- Hemorrhage
- (Emergency) (re)laparotomy
- Pneumonia
- Myocardial infarction
- Mortality

### ***9.3. Risk Minimization Actions***

Additional risks may exist. Risks can be minimized by performing procedures in the appropriate hospital environment, adhering to patient selection criteria, and close monitoring the patient's physiologic status during research procedures and/or follow-up visits. Promptly supplying BSC with all pertinent information required by this protocol may facilitate inter-center communications regarding serious AEs.

### ***9.4. Anticipated Benefits***

Patients may not receive any benefit from participating in this study but this study may provide a future benefit to medical science and other patients. To date there is no broadly accepted standard of practice pertaining to the use of SEMS for Pre-operative management of patients with pancreatic cancer undergoing neoadjuvant therapy.

### ***9.5. Risk to Benefit Rationale***

Based on prior BSC's clinical studies and collected reports in literature to-date, the risk-to-benefit ratio is within reason for foreseeable risks. However, literature reports do not always capture all side effects. Observation and follow up of patients is required as outlined in the protocol.

## **10. Safety Reporting**

### ***10.1. Definitions and Classification***

Adverse event definitions are provided in **Table 4**.

**Table 4: Adverse Event Definitions**

Term	Definition
Adverse Event (AE)  Ref: ISO 14155-2011	
Any untoward medical occurrence, unintended disease or injury, or any untoward clinical signs (including an abnormal laboratory finding) in patients, users or other persons, whether or not related to the investigational medical device. This includes events related to:
 
 
• The investigational medical device or comparator
 
• The procedures involved (study-required)
 
 
For users/other persons, this definition is restricted to events related to the investigational device

Adverse Device Effect (ADE)  Ref: ISO 14155-2011	
Adverse event related to the use of an investigational medical device:
 
 
• This includes adverse events resulting from insufficient or inadequate instructions for the use, deployment, implantation, installation or operation, or any malfunction of the investigational medical device.
 
• This includes any event resulting from use error or from intentional misuse of the investigational medical device.
 

Serious Adverse Event (SAE)  Ref: ISO 14155-2011	
Adverse event that:
 
 
• Led to death,
 
• Led to serious deterioration in the health of the patient, that either resulted in: 
 
◦ a life-threatening illness or injury, or
 
◦ a permanent impairment of a body structure or a body function, or
 
◦ in-patient hospitalization or prolonged hospitalization (of existing hospitalization), or
 
◦ medical or surgical intervention to prevent life-threatening illness or injury or permanent impairment to a body structure or a body function
 
 
 
• Led to fetal distress, fetal death, or a congenital abnormality or birth defect.
 
 
Note : Planned hospitalization for a pre-existing condition, or a procedure required by the protocol, without serious deterioration in health, is not considered a serious adverse event.
 
Note: For SAE reporting requirements see the information below for SADE.

Serious Adverse Device Effect (SADE)  Ref: ISO 14155-2011	
Adverse device effect that has resulted in any of the consequences characteristic of a serious adverse event.
 
Note: All SAEs that could have led to a SADE if suitable action had not been taken or if circumstances had been less fortunate shall be reported as required by the local IRB/EC, national regulations, or the protocol. If

